**Table 15: Safety Lead-in Probability Table**

| True Toxicity Rate | Probability for Dose Escalation in the Safety Lead-in Phase |
|--------------------|---|
| 0.01               | >0.99   |
| 0.05               | 0.97  |
| 0.1                | 0.89  |
| 0.2                | 0.66  |
| 0.4                | 0.23  |

#### 13.3.2 Randomized Arms

The randomized arms will be treated independently, not directly compared. Anti-tumor activity will be measured via disease control rate (DCR), which will be defined as the proportion of patients with complete response (CR), partial response (PR) or stable disease (SD) that persists for  $\geq 4$  months. Radiologic response will be assessed using RECIST v1.1 criteria. With 20 subjects in each treatment arm, there is 79% power using a one-sided alpha of 0.1 to differentiate between an unacceptable DCR of 5% and a desirable DCR of 20%. Observing at least 3 patients with disease control in a treatment arm will be sufficient for the rejection of the null hypothesis in favor of the desirable DCR of 20% and suggesting that further evaluation of this treatment arm is warranted.

While treatment cross-over will be permitted (see **Section 5.1.4**), participants who cross-over will not be considered in the primary endpoint analysis of combination treatment.

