#### **5.6 Duration of Follow Up**

Participants will be followed for 30 days after removal from protocol therapy or until death for serious adverse events, whichever occurs first. Participants removed from protocol therapy for unacceptable adverse event(s) will be followed until resolution or stabilization of the adverse event. After completion of the 30 day follow up period, participants will continue to be followed for 6 months after removal from protocol therapy or until death for survival status only.

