| Radiologic evaluation i    | X  | Radiologic measurements should be performed every 8 weeks (± 7 day scheduling window) |               |                            |                             |                             |                             |                             | X                          |   | Screening, Every 8 weeks, Off Treatment              |
| Tumor Biopsy j             | X  |   |               |                            |                             |                             |                             |                             | X                          |   | Screening, Off Treatment                             |
| PD Marker k                |  | X   |               |                            | X                           |                             | X                           |                             | X                          |   | Screening, Day 1 of all cycles, C1D15, Off Treatment |
| Standard ophthalmic exam l | X  |   |               |                            |                             |                             | X                           |                             |                            |   | N/A  |

|  | Table 11: Study Calendar for the Safety Lead-in Cohort, Arm 1, and Cross-Over Participants |                                    |               |                            |                             |                             |                             |                             |                            |   |  |
|--|---|------------------------------------|---------------|----------------------------|-----------------------------|-----------------------------|-----------------------------|-----------------------------|----------------------------|---|--|
|  | Screening ∞  | Cycle 1 Day 1 a         | Cycle 1 Day 2 | Cycle 1 Day 8 b | Cycle 1 Day 15 b | Cycle 1 Day 22 b | Cycle 2+ Day 1 c | Cycle 2 Day 15 b | Off Treatment d | Every Month Following Treatment Discontinuation | EDC Timepoints ¥                                |

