| ∞ : Cross-over participants do not need to re-screen but must provide re-consent prior to initiating cross-over treatment. First day of combination treatment will be considered C1D1 of cross-over.
See Section 5.1.4 .
¥ : Note: column relevant only for CRF builders.
a. Please refer to Section 5.2.1 .
b. A ± 3 day scheduling window is allowable to account for holidays, adverse weather, vacations, or any other scheduling issues.
c. A ± 7 day scheduling window is allowable to account for holidays, adverse weather, vacations, or any other scheduling issues.
d. Off treatment evaluation. Note: for IND trials, follow up visits or other contact are required in order to identify SAEs during the 30 days following the end of study treatment.
e. Heart rate, respiratory rate, temperature, blood pressure, and oxygen saturation; to be performed prior to study agent dosing.
f. Albumin, alkaline phosphatase, total bilirubin, bicarbonate, BUN, calcium, chloride, creatinine, glucose, potassium, total protein, SGOT [AST], SGPT [ALT], sodium, phosphorus, creatinine phosphokinase (CPK).
g. Serum pregnancy test only required for women of childbearing potential. Childbearing potential defined as any female who has experienced menarche and who has not undergone successful surgical sterilization (hysterectomy, bilateral tubal ligation or bilateral oophorectomy) or is not postmenopausal (defined as amenorrhea >12 consecutive months; or women with a documented plasma follicle-stimulating hormone level >35µU/mL).
h. EKG to be collected during screening, C1D8, on C1D15, C1D22, C2D1, and C3D1 at any time during the study visit, and as clinically indicated. Single EKG to be collected at each time point. QTc to be calculated using Bazett's formula.
i. Radiologic imaging of any disease-involved site.
j. A tumor biopsy is mandatory at baseline for all participants, and optional at the time of disease progression for all participants. Tumor biopsies to be collected as per Section 9.1 . A repeat screening tumor biopsy is not required for cross-over participants (i.e. participants are not required to have a biopsy prior to crossing-over).
k. Blood samples to be collected as per Section 9.2 .
l. To be performed by an ophthalmologist. Exam required during screening and on Cycle 3 Day 1 (± 7 day window). In addition, exam required if participant experiences new or worsening visual disturbances or suspected ocular toxicity while receiving trial treatment.
m. PK sample collection only required on participants enrolled to the Safety Lead-in Cohort and the first six evaluable participants enrolled to Arm 1 . Refer to Section 9.3 for details.
n. Adequate supply of the study agents should be dispensed to account for any pre-planned scheduling delays.
o. Following treatment discontinuation, participants will continue to be followed for survival status only for 6 months or until death, whichever occurs first. Survival status may be verified via medical record review, contact with care providers, or telephone contact with the patient. A ±14 day window is allowed for survival status verifications. |   |                                    |               |                            |                             |                             |                             |                             |                            |   |  |

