## 11. MEASUREMENT OF EFFECT

### 11.1 Antitumor Effect – Solid Tumors

For the purposes of this study, participants should be re-evaluated for response every 8 weeks ( $\pm$  7 day scheduling window). In addition to a baseline scan, confirmatory scans should also be obtained not less than 4 weeks following initial documentation of objective response.

For patients who discontinue protocol treatment prior to disease progression, they will continue to undergo restaging scans every 8 weeks  $\pm$  7 days or earlier if clinically indicated, until the documentation of disease progression.

Response and progression will be evaluated in this study using the new international criteria proposed by the Response Evaluation Criteria in Solid Tumors (RECIST) guideline (version 1.1) [*Eur J Ca* 45:228-247, 2009]. Changes in the largest diameter (unidimensional measurement) of the tumor lesions and the shortest diameter in the case of malignant lymph nodes are used in the RECIST criteria.

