#### 11.1.8 Duration of Response

Duration of overall response: The duration of overall response is measured from the time measurement criteria are met for CR or PR (whichever is first recorded) until the first date that recurrent or progressive disease is objectively documented (taking as reference for progressive disease the smallest measurements recorded since the treatment started, or death due to any cause. Participants without events reported are censored at the last disease evaluation).

Duration of overall complete response: The duration of overall CR is measured from the time measurement criteria are first met for CR until the first date that progressive disease is objectively documented, or death due to any cause. Participants without events reported are censored at the last disease evaluation.

Duration of stable disease: Stable disease is measured from the start of the treatment until the criteria for progression are met, taking as reference the smallest measurements recorded since the treatment started, including the baseline measurements.

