## **13.2 Sample Size, Accrual Rate and Study Duration**

The safety lead-in cohort will enroll a maximum of 12 patients. For the randomized component of the trial, a total of 20 patients will be enrolled to each treatment arm of the trial, for an overall maximum total of 52 patients. Participants will be replaced in the randomized portion of the trial if they withdraw consent for participation before receiving any protocol treatment or rapid disease progression limits their ability to receive any therapy per protocol. We will enroll up to 54 subjects in order to obtain 52 evaluable cases. We expect to complete trial enrollment within 24 months. An additional 4 months will be required to observe the response of the last

participant accrued, for a total length of approximately 28 months for determination of the primary endpoint of DCR. OS is a secondary endpoint of the trial, and participants will continue to be followed for survival status for 6 months following treatment discontinuation or until death.

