#### **13.6.2 Evaluation of the Primary Efficacy Endpoint**

All eligible patients included in the study who receive study medication will be assessed for response, even if there are major protocol therapy deviations. Patients who are replaced due to not receiving any protocol therapy will not be included in efficacy analyses.

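### DCR needs SD for at least 4 months, but an in-window week-16 scan falls short of that, and section 5.6 and the calendar footnotes omit post-treatment scans that section 11.1 requires

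*Combined protocol and SAP*

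**What the plan says.** **Endpoint.** Sections 1.2 and 13.3.2 define DCR in the same words: "which will be defined as the proportion of patients with complete response (CR), partial response (PR) or stable disease (SD) that persists for" at least 4 months. On duration, section 11.1.8 says "Stable disease is measured from the start of the treatment until the criteria for progression are met". It censors response durations at the last disease evaluation but gives SD no such rule. No section converts 4 months into days or names the scan that decides; only the cycle is defined (28 days, section 5.1).

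**Scans.** Tables 11 and 12 both state "Radiologic measurements should be performed every 8 weeks (± 7 day scheduling window", and each adds a radiologic evaluation at the off-treatment visit.

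**After treatment stops.** For patients who stop before progression, section 11.1 says "they will continue to undergo restaging scans every 8 weeks", until progression is documented. Section 5.6 says that, after a 30-day safety period, "participants will continue to be followed for 6 months after removal from protocol therapy or until death for survival status only". Footnote o of Table 11 and footnote n of Table 12 say "participants will continue to be followed for survival status only for 6 months or until death, whichever occurs first".

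**Timing and analysis set.** Section 13.2 allows 4 months after the last accrual, "for a total length of approximately 28 months for determination of the primary endpoint of DCR". Section 13.6.2 says "All eligible patients included in the study who receive study medication will be assessed for response". Section 13.3.2 judges each arm separately: 3 or more of 20 with disease control, 5% against 20%, one-sided alpha 0.1, power 79%.

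**The concern.** The second scan comes too early to show four calendar months of SD, and the third comes well after that point. A patient in SD at week 16 therefore needs either a later scan or a written rule that week 16 is enough. No such rule is written, and two sections on follow-up after treatment do not provide for the later scan. A site that follows section 5.6 and the calendar footnotes stops imaging a patient who leaves treatment without progression. That patient's primary-endpoint data cannot be recovered at analysis. With a threshold of 3 in 20 and an open-label design, the classification of a single patient could settle an arm's result after the data have been seen.

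**Working it through.** **1. The plan's own figure.** With n = 20 and rejection if X ≥ 3, the rejection probability is 1 − Σ C(20,x) pˣ(1−p)²⁰⁻ˣ over x = 0, 1, 2. At p = 0.05 this is 0.0755 and at p = 0.20 it is 0.7939. The stated 79% reproduces, and the attained alpha is below 0.1.

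**2. Scan days.** Assume windows are counted from day 1, so a scan falls on day 7 × week ± 7.

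| Scan | Nominal day | Window |
|---|---|---|
| Week 8 | 56 | 49–63 |
| Week 16 | 112 | 105–119 |
| Week 24 | 168 | 161–175 |

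Four calendar months are 120–123 days depending on the start date (mean 121.75). The latest in-window second scan is 1–4 days short and the nominal one 8–11 days short. If each window ran from the previous scan instead, the second scan would fall on days 98–126 and some would reach four months.

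**3. Who can be classified.**
- SD at week 16 and no progression at a later scan beyond four months: controlled.
- SD at week 16 and progression first found at week 24: controlled, because section 11.1.8 runs SD until the progression criteria are met.
- SD at week 16 and no later scan: undetermined.

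**4. Source A, stopping treatment without progression.** Section 11.1 requires scans until progression. Section 5.6 and the two footnotes provide survival status only. Following the latter can lose the scan after week 16 or, if treatment stops earlier, the week-16 scan as well. The documents give no rate for this in the present trial.

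**5. Source B, late accrual.** Assume analysis at about 28 months and uniform accrual.
- Last accrual months without a week-24 scan: (161 − 121.75)/30.44 = 1.29 to (175 − 121.75)/30.44 = 1.75.
- Accrual rate: 40/24 = 1.67 to 52/24 = 2.17 patients per month.
- Patients without that scan: 1.29 × 1.67 = 2.1 to 1.75 × 2.17 = 3.8 in total, so 1.1–1.9 per arm.
- Only those still in SD are undetermined. At a true DCR of 20% that is about 0.2 × (1 to 2) = 0.2–0.4 per arm.

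**6. Effect on the decision.** As an adverse bound, count all k late patients per arm as failures.

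| k | Power at 20% | Alpha at 5% |
|---|---|---|
| 0 | 0.7939 | 0.0755 |
| 1 | 0.7631 | 0.0665 |
| 2 | 0.7287 | 0.0581 |

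The power differences, 0.031 and 0.065, are the chances that an arm with a true DCR of 20% changes from go to no-go. If one patient is undetermined, that patient decides the arm when exactly 2 of the other 19 are controlled: C(19,2) × 0.2² × 0.8¹⁷ = 0.154 at a true DCR of 20%.

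**7. Effect of the choice of scan.** Assume exponential progression, with 5% and 20% holding at day 121.75. The rate at day t is then p^(t/121.75).

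| Day scored | Null rate | Alternative rate | Type I error | Power |
|---|---|---|---|---|
| 105 | 7.6% | 25.0% | 0.189 | 0.908 |
| 112 | 6.4% | 22.8% | 0.131 | 0.866 |
| 119 | 5.3% | 20.7% | 0.089 | 0.816 |
| 168 | 1.6% | 10.8% | 0.004 | 0.372 |

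**The case against.** The best defence is that week 16 was always meant. Section 13.2 says four months are needed to observe the last participant's response, and four 28-day cycles are 112 days, the nominal second scan. On that reading the late-accrual problem largely disappears. The reading is plausible, but no section states it. If 112 days were the threshold, an in-window scan on days 105–111 would still fall short.

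A reader might also infer that follow-up for DCR ends before the third scan. The documents do not support that. Section 13.2 gives an approximate timeline for the last participant, not a data cut-off or a limit for each patient. Section 14 places the end of study at the last data items or when the outcome data are mature enough. Patients on treatment keep their 8-weekly scans, so most patients in SD at week 16 will have a later one.

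It can further be argued that a default exists: section 13.3.2 counts patients observed with disease control and section 13.6.2 keeps every eligible treated patient, so unobserved control is not counted. That is a fair inference, but it is not written as a rule.

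Finally, section 11.1 is the specific imaging rule and might be taken to prevail. Nothing says that it does, and sites work from the calendar.

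**Conclusion.** The point holds in limited form and should be fixed before DCR is analysed. The endpoint, the scan schedule and the post-treatment follow-up do not fit together for patients in SD at week 16 with no later scan. The conflict between section 11.1 and section 5.6 with the footnotes matters most, because it can lose data for good; its frequency is unknown. Late accrual is a minor source: about 0.2–0.4 undetermined patients per arm at a true DCR of 20%, if analysis is at about 28 months and accrual is uniform.

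Two stronger readings should be resisted. The sample-size calculation is not wrong: 79% is correct for 5% against 20%. Nor is power expected to fall to 76% or 73%; those are bounds that count one or two late patients per arm as failures whatever their status. The scan days assume windows counted from day 1, which section 6.1 favours by keeping the assessment schedule running through dose holds.

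**What to change.** 1. Reconcile section 5.6 and the footnotes to Tables 11 and 12 with section 11.1, so that patients who stop treatment without progression keep the 8-weekly scans section 11.1 already requires, at least through the scan that decides DCR.
2. In sections 1.2 and 13.3.2, name the deciding scan and its window; for example, no progression through the week-16 assessment ± 7 days. Count treated patients without a qualifying scan as not controlled and keep them in the denominator. Align section 13.2 with that scan. The week-16 window ends at day 119 (119/30.44 = 3.91 months), inside the planned 4 months if counted from day 1. If windows ran from the previous scan, it could end at day 126 (4.14 months), outside them.
3. Confirm that 5% and 20% are rates for the endpoint so defined. If they refer to four calendar months, restate the operating characteristics: scoring at day 112 gives type I error of about 0.13, above the planned 0.1, and power of about 0.87 under the exponential assumption.

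Optional clarifications are whether the duration requirement also covers CR and PR, and whether windows are counted from day 1 or from the previous scan.

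Items 1 and 2 cost text changes only, with no extra patients and no scans beyond those section 11.1 requires. Item 3 costs a check, and a restatement if the rates refer to four calendar months. The downside is that a week-16 endpoint is somewhat more lenient than a strict four-calendar-month reading.

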### 13.4 Analysis of Secondary Endpoints

Point estimates and exact binomial 90% confidence intervals will be provided for binary secondary endpoints such as ORR. The method of Kaplan and Meier will be used to estimate overall survival in all patients; and duration of response in those that achieve OR.

### **13.5 Analysis of Exploratory Endpoints**

All participants will have a mandatory pre-treatment biopsy, and an optional time of progression biopsy will be offered to all participants. Non-parametric paired analysis will be conducted to assess the significance of changes between pre-treatment and time of progression samples.

Concordance of drug sensitivity and WTS results will be analyzed. The percentage of pre-treatment biopsies with that are above a 66% sensitivity threshold for organoid sensitivity will be determined. With a sample size of 20 per arm, we will obtain a 95% confidence interval of (36.1%, 80.9%) if we observe 60% (or 12) of the pre-treatment biopsies that are above the threshold.

Agreement between the two biopsies will be analyzed using the Kappa statistics.

